## 2. SYNOPSIS

An open label, multi-center study to evaluate sensory attributes of an antihistamine product		
Primary Objective : 
 
To evaluate perception of cooling sensation of a single dose of a flavored chewable antihistamine tablet
 
		
The Test Product that will be tested is noted below.		
Product (UI # 1613932)	Formula / Actuator Description Identifier	BAY 762211
Loratadine Chewable Tablet (10 mg) (Cool Mint)	
Drug substance
 
Loratadine
 
Excipients
 
Anhydrous Citric Acid
 
Aspartame
 
Colloidal Silicon Dioxide
 
FD&C Blue #1 Aluminum Lake
 
Flavor, CCI [REDACTED]
 
Flavor, CCI [REDACTED]
 
Magnesium Stearate
 
Mannitol
 
Menthol
 
Microcrystalline Cellulose
 
Sodium Starch Glycolate
 
Stearic Acid
	
Comparator Products	Not applicable	
Diagnosis and Main Criteria for Inclusion / Exclusion	Main Inclusion Criteria: 
 
Capable of understanding and providing written informed consent and confidentiality including signatures.
 
Female or male adults aged 18 to 65 years of age inclusive (recruitment to ensure that no less than approximately 40% of each gender is represented in the study population)
 
Be in good general health
 
Previous self-reported sufferers of upper respiratory allergies who at the time of the study are either asymptomatic, symptomatic but not treating and agree to use study medication or symptomatic and treating with an allergy medicine that is not an antihistamine
 
	

	

5. Agree to not use antihistamine products 24 hours before and after the treatment (see medication exclusion list, Appendix 1)

6. Willing to comply with appropriate instructions provided to complete the study

7. Willing to avoid eating food or candy (other than crackers consumed during testing), drinking any liquid other than water, gum chewing and teeth brushing one hour prior to testing

8. Willing to follow and to adhere to the testing instructions as set forth in this protocol.

 
Main Exclusion Criteria:
 
Medication use
 

1. Individuals who have used oral/systemic medications 24 hours before the first administration of test product as listed in the medication exclusion, Appendix 1

2. Individuals who use medications which may influence taste perception as listed in the medication exclusion, Appendix 1

3. Individuals who have received or used an investigational new drug in the last 30 days or have been an active participant in another clinical or market research study in the last 30 days.

 
Medical conditions and history
 

4. Women who are pregnant or thinking of becoming pregnant or are nursing.

5. Participants with congestion at the time of study visit

6. Any self-reported symptoms or conditions that may interfere with the participants ability to complete the evaluation of the product on testing day

7. Any current medical condition that in the opinion of the Investigator or designee may interfere with normal taste and/or temperature perception (e.g., active common cold, sinus infection, bronchial infection, adenoids, paresthesia etc.)

8. History of alcohol or drug abuse (self-reported)

9. History of hypersensitivity or allergic reactions to any ingredients in the test product.

10. Individuals with a history of glaucoma, liver or kidney disease, respiratory conditions such as chronic bronchitis or swallowing difficulties

--	--

	
11. Individuals who are currently wearing any kind of dental braces or with dental work or have cavities and associated pain that may affect their ability to chew a tablet
 
Other exclusion criteria
 
12. Currently working for a market research, flavor house, expert sensorial evaluator, or consumer product company; OR Close affiliation with the investigational site; e.g. a close relative of the investigator, dependent person (e.g. employee or student of the investigational site) or Bayer employee or affiliate; OR They or someone else in the household work for a market research company, an advertising agency, a public relations firm, a pharmaceutical company, as a healthcare professional, or as part of a health care practice.

Study Design	
This study is an open label, multi-center study assessing the cooling attribute of a flavored antihistamine chewable tablet. The study will consist of one site visit where a single dose (10 mg loratadine chewable tablet) of study product will be administered.

Methodology	
Pre-Screening Phase (Electronic or Telephone pre-screening)                  The test site will recruit participants via an IRB approved screener. Potentially eligible participants will be given an appointment time to visit the site. This Process will be 1 to 30 days prior to study start.  Note: No recruiting will be performed unless IRB approval has been obtained.
 
Screening Phase (On-site screening for verification of eligibility)
 
 
• The study staff will screen potential participants to verify they meet the study’s eligibility criteria. Not all participants may fulfill the inclusion/exclusion criteria, so a higher number of participants than needed will be asked to participate in the screening examinations.
 
• After obtaining the participant’s signature on the consent form, screening procedures will be performed and qualifying participants will be enrolled.
 
• If the screening procedures start on the same day the participant signs the informed consent form (ICF), the time of the participant’s signature must be recorded in the participant’s file
 
 
Assessment Phase                  Adequate and appropriate training will be conducted to ensure participants understand the study tasks and how to use the study scales. A nurse practitioner will be on site during the entire dosing period.
 
Visit 1, Day 1 (Assessment Phase)
 
 
• One test product will be provided in a dosing cup to the participant and will be asked to chew completely before swallowing. Participants cannot drink water until end of visit.
 
• Study staff initiates timer as soon as the study medication is administered
 

	
 
• Participant will be asked to indicate if he/she perceives a cooling sensation in each of the locations (mouth, nose and throat) at 10 seconds, 30 seconds and 1 minutes post ingestion of study product
 
• After the 1 minute time point, participants will be asked to complete a brief questionnaire on the sensory attributes of the test product. Participants will be allowed four (4) minutes to complete the questionnaire.
 
• Following the completion of the questionnaire, participants will continue to evaluate perception of cooling sensation in the mouth, nose and throat starting at the 5 minute time point and at 5 minute intervals for 60 minutes
 
• Following completion of all study assessments, participants will be asked open ended questions which will be used for learning purposes
 
• The study visit will last approximately 60-75 minutes.
 
• Adverse events, if applicable, will be recorded
 
• Participants will be reminded to report any unusual or unexpected medical changes within the 24 hour period following administration of the study product to site personnel
 
 
Follow Up Phase
 
 
• At the End of Study, if a participant has an ongoing adverse event, the adverse event will be monitored and recorded and the participant will be contacted during the following week after discharge from the study site.
 

Number of Participants	Approximately 400 adults (100 per location: North East, South, Midwest and West regions within the United States of America)
Primary Variable	
 
• Agreement (strongly agree or somewhat agree) of perception of cooling sensation based on a 5 point agreement scale
 

Plan for Statistical Analysis	
Sensory attributes questionnaire: The percentage of selection of the top 2 choices (strongly agree and somewhat agree) will be determined for each question. This percentage and its 95% confidence interval will be calculated, if the lower bound of the confidence interval is greater than 50%, the statistical majority of agreement will be claimed.
 
Time to perception of cooling and duration of cooling: variables will be analyzed descriptively (Mean, Standard deviation, Median, Mode and Range). The mean time point at which cooling is initially perceived will be claimed as the onset of cooling. The mean time point at which cooling is perceived to last will be claimed as the duration of cooling. Participants who never reach “Yes” in the perception of cooling will be (1) imputed by the maximum study time (60 minutes), and (2) treated as censored and used Kaplan-Meyer to estimate the median time to perception of cooling.

**Table 1 List of Abbreviations**

AE	Adverse Event
CONSORT	Consolidated Standards of Reporting Trials
CRF	Case Report Form
CRO	Contract Research Organization
ICF	Informed Consent Form
IEC	Independent Ethics Committee
IRB	Institutional Review Board
OTC	Over the Counter
SAE	Serious Adverse Event
SoA	Schedule of Activities
SP	Study Protocol
SUSAR	suspected unexpected serious adverse reactions

### 3. INTRODUCTION

Second generation antihistamines like loratadine are used for the temporary relief of symptoms associated with upper respiratory allergies. Several anti-histaminergic drugs are available as over-the-counter (OTC) drugs around the world. In general, these medications are safe and effective when used as directed. Availability as OTC allows consumers to effectively manage their symptoms by following labeled instructions without needing to consult a health care provider.

In addition to efficacy benefits of an over-the-counter product, sensorial benefits may also be of importance for consumer acceptance. Bayer Consumer Health has a currently approved, flavored chewable tablet that contains the antihistamine, loratadine. Participants will be recruited to participate in this study that requires taking the product and evaluating sensory attributes of the product.

## 4. STUDY OBJECTIVES

### Primary Objective

- To evaluate perception of cooling sensation of a single dose flavored chewable antihistamine tablet

## 5. STUDY DESIGN

### 5.1 Design Overview

This study is an open label (participants blinded to brand), multi-center study assessing the sensory attributes of a flavored antihistamine chewable tablet.

The study will consist of one site visit where a single dose of study product will be administered.

Approximately 520 subjects will be screened across 4 sites in the North East, South, Midwest and West regions within the United States of America. With approximately 400 adults completing; 100 per location.

**Visit 1:** participants will present for an onsite screening for inclusion and exclusion criteria prior to the beginning of any product evaluation. Upon qualification and prior to participation in the study, participants will sign an informed consent form.

Qualifying participants will be instructed to chew completely before swallowing, one full dose (10 mg loratadine chewable tablet) during this visit. The study visit will last approximately 60-75 minutes.

A detailed description of study procedures and tabular schedule of evaluations will be found in [Section 9](#).

### 5.2 End of study Definition

A participant is considered to have completed the study if he/she has completed all phases of the study including the last visit or the last scheduled procedure shown in the Schedule of Activities (SoA) ([Section 9.1](#)), including follow up if required.

### Primary completion

The primary completion is defined as the date of completion of all assessments at visit 1.

## 6. STUDY POPULATION

### 6.1 Inclusion Criteria

Only participants who meet all of the following eligibility criteria will be eligible for the study:

1. Capable of understanding and providing written informed consent and confidentiality including signatures.
2. Female or male adults aged 18 to 65 years of age inclusive (recruitment to ensure that no less than approximately 40% of each gender is represented in the study population)

3. Be in good general health
4. Previous sufferers of self-reported upper respiratory allergies who at the time of the study are either asymptomatic, symptomatic but not treating and agree to use study medication or symptomatic and treating with an allergy medicine that is not an antihistamine
5. Agree to not use antihistamine products 24 hours before and after the treatment (see medication exclusion list, [Appendix 1](#))
6. Willing to comply with appropriate instructions provided to complete the study
7. Willing to avoid eating food or candy (other than crackers consumed during testing), drinking any liquid other than water, gum chewing and teeth brushing one hour prior to testing
8. Willing to follow and to adhere to the testing instructions as set forth in this protocol.

## 6.2 Exclusion Criteria

Participants presenting with any of the following will not be eligible for the study:

### Medication use

1. Individuals who have used oral/systemic medication (prescription or non-prescription) 24 hours before the first administration of test product, as listed in the medication exclusion [Appendix 1](#).
2. Individuals who use medications which may influence taste perception as listed in the medication exclusion, [Appendix 1](#)
3. Individuals who have received or used an investigational new drug in the last 30 days or have been an active participant in another clinical or market research study in the last 30 days.

### Medical conditions and history

4. Women who are pregnant or thinking of becoming pregnant or are nursing.
5. Participants with congestion at the time of study visit
6. Any self-reported symptoms or conditions that may interfere with the participants ability to complete the evaluation of the product on testing day
7. Any current medical condition that in the opinion of the Investigator or designee may interfere with normal taste and/or temperature perception (e.g., active common cold, sinus infection, bronchial infection, adenoids, paresthesia etc.)
8. History of alcohol or drug abuse (self-reported)
9. History of hypersensitivity or allergic reactions to any ingredients in the test product.
10. Individuals with a history of glaucoma, liver or kidney disease, respiratory conditions such as chronic bronchitis or swallowing difficulties
11. Individuals who are currently wearing any kind of dental braces or with dental work or have cavities and associated pain that may affect their ability to chew a tablet

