### **Justification of selection criteria**

The selection criteria were chosen to ensure that participants with specific risks for administration of the study drug and/or participants with conditions that may have an impact on the aims of the study are excluded.

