## 7. TEST PRODUCTS

### Test Products to be Administered/Tested

There is one test product to be administered/tested in this study:

**Table 2:** Test Product

Product (UI Number: 1613932)	Strength	Dosage Form or Quantity	Route of Administration
Loratadine Chewable Tablet	10 mg	1 Chewable Tablet*	Oral
*Each tablet to be chewed completely before swallowing. Participants are not allowed to drink water until the end of the visit			
Excipients (identification of potentially allergenic compounds may have to be considered)			
Anhydrous Citric Acid			
Aspartame			
Colloidal Silicon Dioxide			
FD&C Blue #1 Aluminum Lake			
Flavor, CCI [REDACTED]			
Flavor, CCI [REDACTED]			
Magnesium Stearate			
Mannitol			
Menthol			
Microcrystalline Cellulose			
Sodium Starch Glycolate			
Stearic Acid			

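### Ingredient screening covers allergy only, so a participant with a non-allergic reason to avoid the tablet's aspartame can meet every listed criterion and be dosed

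*Combined protocol and SAP*

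**What the plan says.** Aspartame appears in the excipient list twice, in the synopsis and in Table 2 of Section 7. No amount per tablet is given. Table 2 raises excipient risk only as a matter of allergy: "identification of potentially allergenic compounds may have to be considered".

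Every eligible participant is exposed once. Section 5.1 states: "Qualifying participants will be instructed to chew completely before swallowing, one full dose (10 mg loratadine chewable tablet) during this visit".

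Exclusion 9 (Section 6.2, repeated in the synopsis) is the only criterion that refers to the product's ingredients: "History of hypersensitivity or allergic reactions to any ingredients in the test product". The justification paragraph at the end of Section 6.2 says that the criteria were chosen to exclude, among others, "participants with specific risks for administration of the study drug".

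**The concern.** Phenylketonuria is a metabolic disorder of phenylalanine handling, and aspartame supplies phenylalanine. It is not an allergy or a hypersensitivity. Exclusion 9 read as written therefore does not reach it, nor any other non-allergic condition that calls for avoiding a listed excipient. If no other criterion fills the gap, the criteria fall short of their stated purpose for one listed ingredient. At stake is an avoidable exposure for a very small number of people. The primary variable, the confidence interval and the claims built on them are unaffected.

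**Working it through.** The protocol gives no figure to reproduce. The check has two parts: reading the criteria against the ingredient list, and sizing the gap.

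**Step 1. Does any criterion reach a non-allergic reason to avoid an excipient?** There are 8 inclusion and 12 exclusion criteria.

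| Provision | Wording or scope | Reaches phenylketonuria? |
|---|---|---|
| Exclusion 9 | Ingredients, but only allergy or hypersensitivity | No |
| Exclusion 10 | "Individuals with a history of glaucoma, liver or kidney disease, respiratory conditions such as chronic bronchitis or swallowing difficulties" | No; no metabolic disorder is named |
| Exclusion 7 | Investigator's opinion, for conditions that "may interfere with normal taste and/or temperature perception" | Not by its wording; it is not a general safety clause |
| Exclusion 6 | "Any self-reported symptoms or conditions that may interfere with the participants ability to complete the evaluation of the product on testing day" | Not by its wording; it concerns completing the assessment |
| Other exclusions (1–5, 8, 11, 12) | Medicines, recent studies, pregnancy, congestion, substance abuse, dental problems, occupation or affiliation | No |
| Medication exclusion list (Section 14) | Drugs only | No |
| Inclusion 3 | "Be in good general health" | Possibly, at the site's discretion; it is undefined |
| Other inclusions (1, 2, 4–8) | Consent, age, allergy history, antihistamine use, compliance, intake before testing | No |

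One of the 12 exclusions refers to ingredients, and it is limited to allergy. None of the 20 criteria names phenylketonuria or phenylalanine.

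**Step 2. Would the described screening steps bring it to light anyway?**
- Section 8 describes the health eligibility CRF as verifying the inclusion and exclusion criteria. A condition outside those criteria has no stated prompt.
- Section 8 also records current medicines with the reason for use. That could reveal a condition treated with a medicine, but no criterion then says what follows.
- Section 9.3.2 collects medical history only where it bears on eligibility. A condition tied to no criterion is not clearly captured.

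**Step 3. How many participants?** The protocol gives no prevalence, so a range of 1 in 10,000 to 1 in 20,000 is assumed. The planned number is 400 (synopsis; Section 5.1).
- Expected number = N × prevalence.
- 400 × 1/10,000 = 0.04.
- 400 × 1/20,000 = 0.02.

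These figures make no allowance for people who exclude themselves or whom the site declines under inclusion 3, so they lean high for the assumed prevalence. The consequence of one tablet cannot be sized, because the aspartame content is not given.

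**The case against.** The strongest case on the other side is that the gap is negligible and may already be closed. Fewer than one affected participant is expected. Exposure is a single tablet of a product that the Introduction describes as currently approved, and Section 9.2.4 places a nurse practitioner on site throughout dosing. The pre-screener and eligibility CRF were not supplied, the consent pages were removed, and part of the allergy questionnaire is redacted. Any of these could carry a warning. The justification paragraph is a general rationale and does not promise to list every excipient precaution. The hazard itself comes from general medical knowledge and not from the protocol.

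Most of that stands, and it is why this is a minor point. It does not alter the text of Sections 6.1 and 6.2. A consent-form warning would be useful, but it would not be an eligibility criterion.

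Three stronger readings are tempting, and the documents do not support them:
- *Such a participant will certainly be dosed.* Inclusion 3 is undefined, and a site could decline someone under it. A person with well-controlled disease could equally satisfy it, and nothing prompts the site to ask. The supportable statement is that they can be dosed.
- *Participants are kept unaware of the ingredients.* Sections 5.1 and 7.4 conceal the brand; nothing says that the ingredients are withheld. Applying exclusion 9 properly implies some discussion of them.
- *Participants have no possible treatment benefit.* Inclusion 4 admits symptomatic people, and Section 9.5.8 leaves open whether relief occurs during the assessment. That the study does not assess efficacy is a different statement.

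**Conclusion.** The point holds as a small gap in the listed criteria. Ingredient screening is confined to allergy, while the tablet contains an excipient that some people must avoid for another reason, and the stated purpose of the criteria is wider than exclusion 9. The expected number affected is about 0.02 to 0.04 of 400, conditional on the assumed prevalence. The harm from one tablet cannot be judged from the documents. The conclusion rests on the visible eligibility text and on the general medical link between aspartame and phenylketonuria. It does not establish that the screener, CRF or consent form lacks a warning. It is worth correcting because the correction is cheap, not because the risk is shown to be large.

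**What to change.** Reconcile exclusion 9, in Section 6.2 and in the synopsis, with the excipient list in the synopsis and Table 2 and with the justification paragraph. Ingredient screening should then also cover known non-allergic conditions that require avoiding a listed excipient, with phenylketonuria as an example. The exact clinical wording is for the sponsor's medical team. Confirm that the pre-screener and the health eligibility CRF ask about it, and add the question if they do not.

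The cost is one line in the criteria and at most one screening question. The effect on recruitment is negligible, and the analysis does not change.

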### Other exclusion criteria

12. Currently working for a market research, flavor house, expert sensorial evaluator, or consumer product company; OR Close affiliation with the investigational site; e.g. a

close relative of the investigator, dependent person (e.g. employee or student of the investigational site) or Bayer employee or affiliate; OR They or someone else in the household work for a market research company, an advertising agency, a public relations firm, a pharmaceutical company, as a healthcare professional, or as part of a health care practice.

### **Justification of selection criteria**

The selection criteria were chosen to ensure that participants with specific risks for administration of the study drug and/or participants with conditions that may have an impact on the aims of the study are excluded.

## **6.3 Lifestyle/Dietary Restrictions**

Participants will be restricted from eating food or candy (other than crackers consumed during testing), drinking any liquid other than water, gum chewing and teeth brushing one hour prior to testing. During testing, participants cannot drink any liquid including water, chew gum or brush their teeth until the end of the visit; otherwise, there are no lifestyle restrictions.

